11.3 Treatments

Data for study drug administration (rescue medication) and concomitant therapies will be listed by treatment group and patient.

11.4 Analysis of the primary variable(s)

The primary aim of the study is to assess the effect of bimagrumab on fat mass at Week 48 of the treatment period.

11.4.1 Variable(s)

The primary efficacy variable is the change from baseline in fat mass (kg) at Week 48.

Since the week 48 visit is the scheduled EOT visit, and since the EOT assessments are also performed in subjects who discontinue early (see [Section 7.2](#)), only EOT assessments on subjects who completed a full treatment regimen (i.e., those who did not discontinue early) will be included in the primary analysis.

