7.2 Discontinuation of study treatment

Subjects may voluntarily discontinue study treatment for any reason at any time.

The investigator must discontinue study treatment for a given subject if, on balance, he/she believes that continuation would be detrimental to the subject's well-being.

Study treatment *must* be discontinued for an individual subject under the following circumstances:

- Withdrawal of consent
- An infusion reaction that is considered severe
- One or more symptomatic hypoglycemic events necessitating third party rescue and suspected to be related to study drug; if diabetes medication can be appropriately reduced, the study drug may be resumed after stabilization of FPG at the Investigator's discretion
- A serious adverse event (SAE) thought to be related to study drug
- Pregnancy: a positive urine pregnancy test after start of study treatment requires immediate interruption of study treatment until serum hCG is performed and found to be negative
- Any protocol deviation that results in a significant risk to the subject's safety
- Emergence of one or more adverse events that in the judgment of the investigator, taking into account the subject's overall status, prevent the subject from safely continuing in the study

Investigational treatment *may* be discontinued under the following circumstances:

- Breaking of the blind (inadvertently or for emergency reasons)
- Use of prohibited treatment as described in the protocol

Subjects who discontinue study treatment should **NOT** be considered withdrawn from the study UNLESS they withdraw their consent. They should return approximately 4 weeks after their last dose for the EoT visit (Visit 113). The EoS visit (Visit 199) should be scheduled

4 weeks after EoT. If they fail to return for these assessments for unknown reasons, every effort should be made to contact them as specified in [Section 7.4](#).

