11.4.2 Statistical model, hypothesis, and method of analysis

The study design enables evaluation of efficacy based on the following dual criteria 1) statistical significance (superior treatment effect, 1-sided 10% level) in fat mass; and 2) clinical relevance of the change in fat mass (estimated median treatment effect of 5% or more). Weight loss of 5% has been shown to translate into clinical benefit in an overweight/obese population with T2D (Franz et al 2015). Fat mass loss of a similar magnitude to the weight loss is expected to translate into similar clinical benefits (such as on glycemic control) in a similar population.

The randomization will be stratified by BMI category (≥ 28.0 kg/m² and ≤ 33.0 kg/m², >33.1 kg/m² to ≤ 40.0 kg/m²) in order to achieve an approximate balance of BMI distribution across the two treatment groups. The cutoff value of 33 kg/m² represents the expected median BMI in that population (based on internal data); therefore the two randomization strata are expected to be of similar size. However, equal size strata will not be enforced. A minimum of 10 patients will be targeted for enrollment in the smaller stratum to ensure accurate precision on the treatment effect in both strata (see Section 11.7).

The primary endpoint will be analyzed using a mixed effects model. This model will have change from baseline in kg fat mass as the dependent variable, treatment arm, time, time*treatment interaction as fixed effects, and a subject level random intercept. Baseline fat mass and baseline BMI value may be included in the model as covariates. Data collected from both randomization strata (BMI category at randomization) will be included in the model. The change from baseline (absolute) in kg fat mass at Week 48 will be estimated from that model and will be summarized graphically and in tabular form. No transformation (logarithmic or otherwise) of body weight will be done for analysis. An unstructured within-subject covariance will be used.

The evaluation of efficacy is based on the following dual criteria:

1. statistical significance (superior treatment effect, 1-sided 10% level) in fat mass; and
2. clinical relevance of the change in fat mass (estimated median treatment effect of 5% or more) at Week 48.

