11.4.3 Handling of missing values/censoring/discontinuations

The primary analysis model described above is valid under the assumption of data missing at random. If the dropout rate is greater than 10% in any arm, other analysis methods will be used to assess the sensitivity of the results to different methods for missing data handling.

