11.7 Sample size calculation

A sample size of 68 recruited subjects (34 receiving active treatment and 34 placebo) is selected to enable at least 48 completers, assuming a dropout rate of maximum 30%.

A sample size of 24 completers per group (total of 48 patients) provides about 70% power (see [Table 11-1](#)) to pass the criteria described above for fat mass (significant reduction at the 1-sided 10% level (compared to placebo) and an estimated median placebo-adjusted reduction of at least 5%). Assumptions used for these calculations include a true placebo-adjusted fat loss of 6% (standard deviation 6.5%, CBYM338X2206). The associated type I error is about 1% ([Table 11-1](#)).

Because weight loss interventions in overweight/obese diabetic patients result in ~ 15% lower magnitude of response compared to overweight/obese non-diabetic patients ([Franz et al 2007](#)), we made the assumption that bimagrumab could have a 6% true effect on fat loss in overweight and obese diabetic patients (this is about 15% lower than the 7.2% effect observed in overweight and obese pre-diabetics (CBYM338X2206)).

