#### 6.1.1 Variables

The primary efficacy variable is the change from baseline in fat mass (kg) at Week 48 of the treatment period. No transformation of (logarithmic or otherwise) will be done for analysis.

Since the week 48 visit is the scheduled EOT visit, and since the EOT assessments are also performed in subjects who discontinue early, only EOT assessments on subjects who completed a full treatment regimen (i.e., those who did not discontinue early) will be included in the primary analysis.

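### The primary analysis drops every early end-of-treatment DXA, and the SAP drops the patient as well; the Week 48 difference is biased if stopping differs between arms

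*Protocol*

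**What the plan says.** **Collection.** Protocol 7.2 keeps patients who stop treatment in the study: "They should return approximately 4 weeks after their last dose for the EoT visit (Visit 113". Table 8-1, footnote 9, gives early stoppers the Visit 113 assessments, which include DXA. The scheduled DXA scans are at baseline, Days 56, 168 and 336 (Weeks 8, 24 and 48) and end of study.

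**Use.** Protocol 11.4.1 states that "only EOT assessments on subjects who completed a full treatment regimen (i.e., those who did not discontinue early) will be included" in the primary analysis. SAP 6.1.1 repeats it: "only EOT assessments on subjects who completed a full treatment regimen". Nothing in the readable text returns an early scan at the week it was taken. SAP 6.1.3 models time as categorical with unstructured covariance.

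**Population.** SAP 6.1.3.1 ends by limiting the final analysis to patients who did not discontinue early and whose end-of-study visit lies within 8 weeks ± 10 days of the Week 48 assessment. The Protocol has no such sentence.

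**Justification.** Protocol 11.4.3 calls the primary model "valid under the assumption of data missing at random"; SAP 6.1.3.1 says the same. Dropout above 10% in any arm triggers sensitivity analyses whose method is not fixed.

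**The concern.** An early scan is not a Week 48 value, and the plan is right not to count it as one. But the rule removes it altogether. It is an on-treatment measurement on a known day, as far from the last dose as a completer's Week 48 scan, and the observation closest to the decision to stop. Missing at random is conditional on the data in the model. If stopping follows response since the last retained scan, deleting that observation takes away what would have explained the missing Week 48 value.

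The SAP sentence makes this worse. It conditions the analysis on a post-randomisation event and also discards stoppers' Week 8 and Week 24 scans, leaving a longitudinal model little missing Week 48 data to handle. The two documents therefore describe different primary analyses.

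At stake is the estimate judged against "clinical relevance of the change in fat mass (estimated median treatment effect of 5% or more) at Week 48".

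**Working it through.** **1. Timing.** Last dose on Day 28: end-of-treatment visit at 28 + 28 = Day 56, the Week 8 visit. Last dose on Day 140: 140 + 28 = Day 168, the Week 24 visit. Completer: 308 + 28 = Day 336. The interval from dosing is the same. An early stopper's end-of-study visit comes 4 weeks after end of treatment (Protocol 7.2); a completer's comes 392 − 336 = 56 days after. The SAP window of 46 to 66 days therefore also screens out early stoppers.

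**2. How many.** Protocol 11.7 allows 30% dropout: 0.30 × 68 ≈ 20 patients. In the simulated stopping patterns, about 20% of stoppers (about 4 patients) have their early scan at Week 8 or 24. About 21 to 31% (4 to 6 patients) have no usable post-baseline scan under the Protocol rule.

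**3. The plan's power.** Inputs: "Assumptions used for these calculations include a true placebo-adjusted fat loss of 6% (standard deviation 6.5%, CBYM338X2206" and "A sample size of 24 completers per group (total of 48 patients) provides about 70% power".
- SE = 6.5 × √(2/24) = 1.876.
- One-sided 10% significance needs an estimate above 1.282 × 1.876 = 2.40, so the 5% threshold binds.
- Power = Φ((6 − 5)/1.876) = 0.703, which reproduces the stated figure.

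Because the threshold binds, a bias in the estimate moves the decision directly.

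**4. Bias.** Simulation on the percent scale: true difference 6, SD 6.5, DXA at Weeks 8, 24 and 48, stopping possible at each 4-weekly visit, about 30% dropout. Assumed, not in the documents: the covariance shape, and log-odds of stopping of 0.15 to 0.30 per point less fat loss at that visit. The last column is Φ((estimate − 5)/1.876), holding the plan's SE.

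| Stopping | Estimate, Protocol rule | Chance of reaching 5 |
|---|---|---|
| Unrelated to response | 6.0 | 70% |
| Same response dependence, 30% in each arm | 6.00 to 6.02 | 70 to 71% |
| One common hazard (placebo 35–38%, bimagrumab 22–25%) | 5.86 to 5.62 | 68 to 63% |
| Response-driven on placebo only | 5.67 to 5.35 | 64 to 57% |
| Response-driven on bimagrumab only | 6.33 to 6.61 | 76 to 80% |

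The SAP completers rule gives roughly 4.3 (placebo only) to 7.4 (bimagrumab only), or 35% to 90% by the same formula. Using each early scan at its actual week gives 6.00 to 6.05, with an SE about 4% smaller than under the Protocol rule.

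**5. Cross-check.** A second set-up had stopping at Weeks 12 to 44, log-odds 1 per SD of poorer response, and overall dropout 30%. The order of estimates is both arms, placebo only, bimagrumab only.
- Protocol rule: 5.55, 4.96, 6.75.
- SAP rule: 5.27, 4.34, 7.20.
- Actual week: 6.08, 6.11, 5.88.
- Protocol rule at other strengths: 5.56 to 6.39 at log-odds 0.5, and 3.93 to 7.38 at log-odds 2.
- Stopping driven only by the retained Week 8 or 24 value: the Protocol rule stays at 6.0 to 6.1, while the SAP rule gives 4.9 to 6.9.
- No true effect, response-driven stopping in one arm only: a spurious difference of 0.9 to 1.0 points (Protocol) or about 1.5 (SAP). The same stopping in both arms gives none.

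**The case against.** **Response-driven stopping need not bias the difference.** This stands for the Protocol rule. With equal dropout and equal dependence on response, both arm means shift alike and the contrast does not move. A reader might infer that any response-driven stopping biases the result, or that the effect is always understated. Neither follows: the arms must differ, and the documents settle neither whether they will nor in which direction. Protocol 11.7 plans 24 completers per group, which implies similar dropout in each arm.

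**The mechanism is uncertain.** DXA is blinded to patient and investigator (Protocol 8.5.2.1), and Protocol 1.1 reports that body weight was unchanged after a single dose despite fat loss. Stopping on current fat change is therefore an assumption. However, weight is measured at dosing visits and patients are coached on weight loss, so it is a plausible one.

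**The actual-week model has its own weaknesses.** Under response-driven stopping in one arm, with only 60% of stoppers returning for the scan, it leaves about 0.13 to 0.27 points of bias; with a wrong covariance, 0.17 to 0.36. If the bimagrumab effect plateaus after Week 36, a mean that is linear between visits adds about 0.15 points even when stopping is unrelated to response. That is a good reason not to replace the pre-specified categorical-time, unstructured model.

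**The plan already has sensitivity analyses.** It does, and 30% dropout would trigger them. They fix no method, do not mention the early scans and leave the primary estimate unchanged. Some SAP text after the model and the supportive analyses is redacted, so a relevant analysis may exist there.

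**The SAP sentence may only be meant to identify valid Week 48 scans.** Possibly, but it speaks of including patients, not scans, and a programmer would follow the words.

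**Conclusion.** The concern holds in a limited form. Both documents discard planned, on-treatment scans that could be used, and SAP 6.1.3.1 as written turns the primary analysis into a completers analysis that does not fit its missing-at-random justification. The Protocol rule costs about 4% of the SE relative to an actual-week model, whatever drives stopping. Its bias is conditional: understated if poor responders on placebo stop more, overstated if poor responders on bimagrumab stop more. Against a true 6, the range is roughly 5.4 to 6.6 under the Protocol rule and 4.3 to 7.4 under the SAP rule, at 30% dropout and log-odds of 0.15 to 0.30 per point. Stopping strength and covariance are assumptions, and stronger dependence widens the range.

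A reader might also infer that the Protocol itself excludes stoppers entirely. It does not: 11.4.1 restricts only end-of-treatment assessments, so their Week 8 and Week 24 scans can stay. Nor is the Protocol model biased if stopping depends only on those retained values. The study is non-confirmatory, but it informs development decisions, and a correction needs no new data.

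**What to change.** 1. **SAP 6.1.3.1:** delete the closing sentence that limits the final analysis to patients who did not stop early. State that all scheduled post-baseline DXA values of early stoppers stay in the model. Without this step the other two have no effect.
2. **Protocol 11.4.1 and SAP 6.1.1:** state that an early end-of-treatment DXA is never a Week 48 value, but that one falling on the Week 8 or Week 24 visit is used as that visit's value. This fits the existing categorical-time, unstructured model.
3. **SAP 6.1.3.2:** name a sensitivity analysis that uses every early end-of-treatment DXA at its actual study week, with a continuous-time mean and parametric covariance. Report its Week 48 contrast beside the primary one.

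The cost is wording and some programming. Step 2 recovers only about 20% of stoppers' early scans, so most of any bias would remain in the primary estimate. Step 3 is meant to show that bias, at the price of assumptions about the time course and covariance that should be written down in advance.

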11.4.2 Statistical model, hypothesis, and method of analysis

The study design enables evaluation of efficacy based on the following dual criteria 1) statistical significance (superior treatment effect, 1-sided 10% level) in fat mass; and 2) clinical relevance of the change in fat mass (estimated median treatment effect of 5% or more). Weight loss of 5% has been shown to translate into clinical benefit in an overweight/obese population with T2D (Franz et al 2015). Fat mass loss of a similar magnitude to the weight loss is expected to translate into similar clinical benefits (such as on glycemic control) in a similar population.

The randomization will be stratified by BMI category (≥ 28.0 kg/m² and ≤ 33.0 kg/m², >33.1 kg/m² to ≤ 40.0 kg/m²) in order to achieve an approximate balance of BMI distribution across the two treatment groups. The cutoff value of 33 kg/m² represents the expected median BMI in that population (based on internal data); therefore the two randomization strata are expected to be of similar size. However, equal size strata will not be enforced. A minimum of 10 patients will be targeted for enrollment in the smaller stratum to ensure accurate precision on the treatment effect in both strata (see Section 11.7).

The primary endpoint will be analyzed using a mixed effects model. This model will have change from baseline in kg fat mass as the dependent variable, treatment arm, time, time*treatment interaction as fixed effects, and a subject level random intercept. Baseline fat mass and baseline BMI value may be included in the model as covariates. Data collected from both randomization strata (BMI category at randomization) will be included in the model. The change from baseline (absolute) in kg fat mass at Week 48 will be estimated from that model and will be summarized graphically and in tabular form. No transformation (logarithmic or otherwise) of body weight will be done for analysis. An unstructured within-subject covariance will be used.

The evaluation of efficacy is based on the following dual criteria:

1. statistical significance (superior treatment effect, 1-sided 10% level) in fat mass; and
2. clinical relevance of the change in fat mass (estimated median treatment effect of 5% or more) at Week 48.

11.4.3 Handling of missing values/censoring/discontinuations

The primary analysis model described above is valid under the assumption of data missing at random. If the dropout rate is greater than 10% in any arm, other analysis methods will be used to assess the sensitivity of the results to different methods for missing data handling.

11.4.4 Sensitivity analyses

Other models may be used (such as pattern-mixture models) if the dropout rate is higher than expected, in order to assess sensitivity of the primary efficacy conclusions to missing data. If a treatment effect in fat mass or HbA1c materializes, then it will be investigated whether this finding is robust under an assumption of informative drop-out; that the subjects who drop out would likely not have experienced a treatment benefit.

11.5 Analysis of secondary variable(s)

Company Confidential Information

11.5.1 Efficacy / Pharmacodynamics

Company Confidential Information

11.5.2 Safety

Vital signs

All vital signs data will be listed by treatment group, patient, and visit and if ranges are available, abnormalities (and relevant orthostatic changes) will be flagged. Summary statistics will be provided by treatment and visit.

ECG evaluations

All ECG data will be listed by treatment group, patient and visit; abnormalities will be flagged. Summary statistics will be provided by treatment and visit.

Clinical laboratory evaluations

All laboratory data will be listed by treatment group, patient, and visit and if normal ranges are available, abnormalities will be flagged. Summary statistics will be provided by treatment and visit.

Adverse events

All information obtained on adverse events will be displayed by treatment group and patient.

The number and percentage of patients with adverse events will be tabulated by body system and preferred term with a breakdown by treatment. A patient with multiple adverse events within a body system is only counted once towards the total of this body system.

Other safety evaluations

Company Confidential Information

11.5.3 Pharmacokinetics

Bimagrumab serum concentration data will be listed by treatment, patient, and visit/sampling time point.

PK parameters will be listed by treatment group, patient, visit/sampling time, and dose number. Descriptive summary statistics will include mean (arithmetic and geometric), SD, and CV (arithmetic and geometric), median, minimum, maximum and 90% CI. A geometric mean will not be reported if the dataset includes zero values. An exception to this is Tmax where median, minimum and maximum will be presented. Summary statistics will include mean (arithmetic and geometric), SD, CV (arithmetic and geometric), median, minimum and maximum.

11.5.4 Pharmacokinetic / pharmacodynamic interactions

Graphical exploration of bimagrumab PK parameters versus fat mass will be provided. Other graphical exploration may be done as appropriate.

11.5.5 Other assessments

Immunogenicity

All immunogenicity results will be listed by treatment group, subject and visit.

11.6 Analysis of exploratory variables

Company Confidential Information

Company Confidential Information

11.7 Sample size calculation

A sample size of 68 recruited subjects (34 receiving active treatment and 34 placebo) is selected to enable at least 48 completers, assuming a dropout rate of maximum 30%.

A sample size of 24 completers per group (total of 48 patients) provides about 70% power (see [Table 11-1](#)) to pass the criteria described above for fat mass (significant reduction at the 1-sided 10% level (compared to placebo) and an estimated median placebo-adjusted reduction of at least 5%). Assumptions used for these calculations include a true placebo-adjusted fat loss of 6% (standard deviation 6.5%, CBYM338X2206). The associated type I error is about 1% ([Table 11-1](#)).

Because weight loss interventions in overweight/obese diabetic patients result in ~ 15% lower magnitude of response compared to overweight/obese non-diabetic patients ([Franz et al 2007](#)), we made the assumption that bimagrumab could have a 6% true effect on fat loss in overweight and obese diabetic patients (this is about 15% lower than the 7.2% effect observed in overweight and obese pre-diabetics (CBYM338X2206)).

11.8 Power for analysis of key secondary variables

The power to pass the criteria for HbA1c (significant reduction and an estimated median placebo-adjusted reduction of at least 0.5%) is about 73%. Assumptions used for these calculations include a true placebo-adjusted HbA1c reduction of 0.7% (standard deviation 1.11%, internal data). The associated type I error is about 6%.

11.9 Interim analyses

Company Confidential Information

Company Confidential Information

12 Ethical considerations

12.1 Regulatory and ethical compliance

This clinical study was designed and shall be implemented, executed and reported in accordance with the ICH Harmonized Tripartite Guidelines for Good Clinical Practice, with applicable local regulations (including European Directive 2001/20/EC, US Code of Federal Regulations Title 21, and Japanese Ministry of Health, Labor, and Welfare), and with the ethical principles laid down in the Declaration of Helsinki.

